Appendix B. eSerious Event Contingency Form

 Study # 20170173 AMG 397		Electronic Serious Adverse Event Contingency Report Form For Restricted Use																				
Reason for reporting this event via fax The Clinical Trial Database (eg, Rave):  Is not available due to internet outage at my site  Is not yet available for this study  Has been closed for this study																						
FAX # JS: [contact]																						
1. SITE INFORMATION																						
Site Number		Investigator			Country																	
Reporter		Phone Number		Fax Number																		
2. SUBJECT INFORMATION																						
Subject ID Number		Age at event onset		Sex	Race	If applicable, provide End of Study date																
If this is a follow-up to an event reported in the EDC system (eg, Rave), provide the adverse event term: _____ and start date: Day ____ Month ____ Year ____																						
3. SERIOUS ADVERSE EVENT																						
Provide the date the Investigator became aware of this information: Day ____ Month ____ Year ____																						
Serious Adverse Event diagnosis or syndrome If diagnosis is unknown, enter signs / symptoms and provide diagnosis, when known, in a follow-up report  List one event per line. If event is fatal, enter the cause of death. Entry of "death" is not acceptable, as this is an outcome.	Date Started		Date Ended		Check only if event occurred before first dose of IP  Is event serious?   Yes  No	Serious enter Serious Criteria code (see codes below)	Relationship Is there a reasonable possibility that the Event may have been caused by IP or an Amgen device used to administer the IP?	Outcome of Event -Resolved -Not resolved -Fatal -Unknown  Check only if event is related to study procedure eg, biopsy														
	Day	Month	Year	Day					Month	Year	
 
 								
 
 No	Yes	No	Yes	No	Yes	No	Yes	
 
									No	Yes	No
																						
No	Yes	No	Yes	No	Yes	No	Yes															
Serious Criteria: 01 Fatal      02 Immediately life-threatening      03 Required/prolonged hospitalization      04 Persistent or significant disability /incapacity      05 Congenital anomaly / birth defect      06 Other medically important serious event																						
4. Was subject hospitalized or was a hospitalization prolonged due this event?  No  Yes If yes, please complete all of Section 4																						
Date Admitted				Date Discharged																		
Day		Month		Year		Day		Month		Year												
5. Was IP/drug under study administered/taken prior to this event?  No  Yes If yes, please complete all of Section 5																						
IP/Amgen Device:	Date of Initial Dose		Date of Dose		Dose	Route	Frequency	Action Taken with Product	Lot # and Serial #													
	Day	Month	Year	Day	Month	Year		01 Still being Administered 02 Permanently discontinued 03 Withheld														
<<IP/Device>>									Lot # _____  Unknown Serial # _____  Unavailable / Unknown													
<<IP/Device>>									Lot # _____  Unknown Serial # _____  Unavailable / Unknown													

Approved

AMGEN Study # 20170173 AMG 397	Electronic Serious Adverse Event Contingency Report Form For Restricted Use
---	--

	Site Number	Subject ID Number													
6. CONCOMITANT MEDICATIONS (eg, chemotherapy) Any Medications?  No  Yes If yes, please complete:															
Medication Name(s)	Start Date			Stop Date			Co-suspect		Continuing		Dose	Route	Freq.	Treatment Med	
	Day	Month	Year	Day	Month	Year	No	Yes	No	Yes				No	Yes
7. RELEVANT MEDICAL HISTORY (include dates, allergies and any relevant prior therapy)															
8. RELEVANT LABORATORY VALUES (include baseline values) Any Relevant Laboratory values?  No  Yes If yes, please complete:															
Date	Test	Unit													
	Day														Month
9. OTHER RELEVANT TESTS (diagnostics and procedures) Any Other Relevant tests?  No  Yes If yes, please complete:															
Date	Additional Tests				Results				Units						
Day	Month	Year													

Approved

AMGEN Study # 20170173 AMG 397	Electronic Serious Adverse Event Contingency Report Form For Restricted Use
---	--

	Site Number	Subject ID Number	
10. CASE DESCRIPTION (Provide narrative details of events listed in section 3) Provide additional pages if necessary. For each event in section 3, where relationship=Yes, please provide rationale.			
Signature of Investigator or Designee - I confirm by signing this report that the information on this form, including seriousness and causality assessments, is being provided to Amgen by the investigator for this study, or by a Qualified Medical Person authorized by the investigator for this study.		Title	Date

Approved

**1. Case Administrative Information**

Protocol/Study Number: AMG 397 20170173

Study Design:  Interventional  Observational (If Observational:  Prospective  Retrospective)

**3. Subject Information**

Subject ID # \_\_\_\_\_ Subject Gender:  Female  Male Subject DOB: mm     / dd     / yyyy    

**4. Amgen Product Exposure**

Amgen Product	Dose at time of conception	Frequency	Route	Start Date
				mm     / dd     / yyyy    

Was the Amgen product (or study drug) discontinued?  Yes  No  
 If yes, provide product (or study drug) stop date: mm     / dd     / yyyy      
 Did the subject withdraw from the study?  Yes  No

**5. Pregnancy Information**

Pregnant female's LMP mm     / dd     / yyyy      Unknown  
 Estimated date of delivery mm     / dd     / yyyy      Unknown  N/A  
 If N/A, date of termination (actual or planned) mm     / dd     / yyyy      
 Has the pregnant female already delivered?  Yes  No  Unknown  N/A  
 If yes, provide date of delivery: mm     / dd     / yyyy      
 Was the infant healthy?  Yes  No  Unknown  N/A  
 If any Adverse Event was experienced by the infant, provide brief details: \_\_\_\_\_  
 \_\_\_\_\_  
 \_\_\_\_\_

**1. Case Administrative Information**

Protocol/Study Number: AMG 397 20170173

Study Design:  Interventional  Observational (If Observational:  Prospective  Retrospective)

**3. Subject Information**

Subject ID # \_\_\_\_\_ Subject Date of Birth: mm \_\_\_\_ / dd \_\_\_\_ / yyyy \_\_\_\_

**4. Amgen Product Exposure**

Amgen Product	Dose at time of breast feeding	Frequency	Route	Start Date
				mm ____ / dd ____ / yyyy ____

Was the Amgen product (or study drug) discontinued?  Yes  No

If yes, provide product (or study drug) stop date: mm \_\_\_\_ / dd \_\_\_\_ / yyyy \_\_\_\_

Did the subject withdraw from the study?  Yes  No

**5. Breast Feeding Information**

Did the mother breastfeed or provide the infant with pumped breast milk while actively taking an Amgen product?  Yes  No

If No, provide stop date: mm \_\_\_\_ / dd \_\_\_\_ / yyyy \_\_\_\_

Infant date of birth: mm \_\_\_\_ / dd \_\_\_\_ / yyyy \_\_\_\_

Infant gender:  Female  Male

Is the infant healthy?  Yes  No  Unknown  N/A

If any Adverse Event was experienced by the mother or the infant, provide brief details: \_\_\_\_\_

#### Appendix D. Operating Characteristics for 2-Parameter BLRM Design

The operating characteristics of the two-parameter BLRM design were evaluated via simulation. The cohort size was fixed to 2 or 4 subjects. The initial multiple subject dose level is 80 mg and subsequent doses were selected based on the following rules:

After each cohort, the next dose is the one with the highest probability of the target TPI, subject to the overdose control limits.

Dose escalation was stopped given 1 or more of the following conditions:

- There have been at least 6 subjects treated at the dose recommended by the model.
- A maximum number of 30 subjects are evaluated

A total of 6 dose levels (unit: mg) were considered: 80, 160, 240, 320, 480, 640 in these simulations of the multiple subject cohorts (80, 160, 320 and 640 are planned dose levels with 240 and 480 possible intermediate dose levels).

The design was evaluated for 3 possible dose-response scenarios: “Low”, “Mid”, and “High” MTD. [Table 1](#) shows the dose level and true probability of DLT for each scenario used in the simulated studies estimating the MTD. [Table 2](#) and [Table 3](#) report the operating characteristics from 1,000 simulated studies estimating the MTD when the target TPI is (0.20, 0.33]; [Table 2](#) reports characteristics when the overdose control limit is 0.40 probability of an excessive or unacceptable TPI while [Table 3](#) reports a limit of 0.25 probability of an excessive or unacceptable TPI.

**Table 1. True Probability of DLT by Scenario for Simulated Studies Estimating MTD**

Dose Level	80	160	240	320	480	640
MTD Scenario						
High	0.04	0.08	0.11	0.18	0.25	0.33
Mid	0.06	0.11	0.18	0.25	0.33	0.45
Low	0.09	0.18	0.25	0.33	0.45	0.55

DLT = dose-limiting toxicity; MTD = maximum tolerated dose.

Approved

**Table 2. Operating Characteristics by Scenario for Simulated Studies Estimating the MTD When the Target TPI is (0.20, 0.33)  
 Overdose Control Limit is 0.40 Probability of an Excessive or Unacceptable TPI**

MTD Scenario	High		Mid		Low	
	4 subjects per cohort	2 subjects per cohort	4 subjects per cohort	2 subjects per cohort	4 subjects per cohort	2 subjects per cohort
Number of Subjects	24	16	24	16	24	16
Median (IQR)	(20 to 28)	(12 to 18)	(20 to 28)	(14 to 18)	(20 to 28)	(14 to 18)
Number of DLTs	4	3	5	4	6	4
Median (IQR)	(3 to 5)	(2 to 4)	(4 to 6)	(3 to 5)	(4 to 7)	(3 to 6)
Proportion of DLT (%)	18	19	21	25	25	29
Median (IQR)	(13 to 21)	(14 to 25)	(19 to 25)	(19 to 29)	(21 to 30)	(25 to 33)
Percentage of studies recommending dose with DLT probability of:						
≤ 10%	2.7	3.3	4.2	4.5	9.3	12.2
> 10% and ≤ 20%	23.4	19.7	12	10.7	17.5	13.5
> 20% and ≤ 33%	73.9	77.0	72.4	66.7	57.2	50.7
> 33%	0	0	11.4	18.1	16.0	23.6
Probability of identifying MTD to have 15% to 33% DLT probability	94.8	95.0	80.3	72.6	74.7	64.2

DLT = dose-limiting toxicity; IQR = interquartile range; MTD = maximum tolerated dose; TPI = toxicity probability interval.

EAST version 6.4 software used to generate 1,000 simulated clinical trials for each scenario.

Approved

**Table 3. Operating Characteristics by Scenario for Simulated Studies Estimating the MTD When the Target TPI is (0.20, 0.33)  
 Overdose Control Limit is 0.25 Probability of an Excessive or Unacceptable TPI**

MTD Scenario	High		Mid		Low	
	4 subjects per cohort	2 subjects per cohort	4 subjects per cohort	2 subjects per cohort	4 subjects per cohort	2 subjects per cohort
Number of Subjects	24	14	24	14	20	14
Median (IQR)	(20 to 28)	(12 to 16)	(20 to 28)	(12 to 18)	(16 to 24)	(10 to 18)
Number of DLTs	4	3	4	3	5	3
Median (IQR)	(3 to 5)	(2 to 3)	(3 to 6)	(2 to 4)	(4 to 6)	(2 to 5)
Proportion of DLT (%)	17	19	20	22	25	28
Median (IQR)	(13 to 21)	(14 to 25)	(17 to 25)	(18 to 29)	(20 to 29)	(22 to 36)
Percentage of studies recommending dose with DLT probability of:						
≤ 10%	4.7	10.7	5.3	15.5	16.9	28.9
> 10% and ≤ 20%	34.0	30.7	14.8	11.7	18.8	14.2
> 20% and ≤ 33%	61.3	58.6	72.2	67.7	54.5	42.7
> 33%	0	0	7.7	5.1	9.8	14.2
Probability of identifying MTD to have 15% to 33% DLT probability	93.5	87.9	79.9	72.9	73.3	56.9

DLT = dose-limiting toxicity; IQR = interquartile range; MTD = maximum tolerated dose; TPI = toxicity probability interval.

EAST version 6.4 software used to generate 1,000 simulated clinical trials for each scenario.

Approved

**Appendix E. International Myeloma Working Group Uniform Response Criteria for Multiple Myeloma (IMWG-URC)**

Response Subcategory a	Multiple Myeloma Response Criteria
sCR b	
 
• CR as defined below and
 
• Normal SFLC ratio and
 
• Absence of clonal cells in bone marrowc by immunohistochemistry or immunofluorescencec
 

CR b	
 
• Negative immunofixation on the serum and urine and
 
• Disappearance of any soft tissue plasmacytomas and
 
• < 5% plasma cells in bone marrowc
 

VGPR b	
 
• Serum and urine M-protein detectable by immunofixation but not on electrophoresis
 
or
 
• ≥ 90% reduction in serum M-protein with urine M-protein level < 100 mg/24 hours
 
• If the serum and urine M-protein are not measurable, a decrease of ≥ 90% in the difference between the involved and uninvolved FLC levels required in place of the M-protein criteria. However, documentation of VGPR requires collection and analysis of 24 hour urine sample for UPEP and immunofixation and confirmed to be negative.
 
• If present at Baseline, a ≥ 50% reduction in the size of soft tissue plasmacytomas is also required.
 

PR b	
 
• ≥ 50% reduction of serum M-protein and reduction in 24-hour urinary M-protein by ≥ 90% or to < 200 mg/ 24 h
 
• If the serum and urine M-protein are unmeasurable, a ≥ 50% decrease in the difference between involved and uninvolved FLC levels is required in place of the M-protein criteria.
 
• If serum and urine M-protein are not measurable, and serum free light assay is also not measurable, ≥ 50% reduction in plasma cells is required in place of M-protein, provided baseline bone marrow cell percentage was ≥ 30%
 
• If present at Baseline, a ≥ 50% reduction in the size of soft tissue plasmacytomas is also required
 

MR	
 
• 25%–49% reduction in the level of serum M-protein and a 50%–89% reduction in 24 hour urinary M-protein, which still exceeds 200 mg per 24 hours
 
• If the serum and urine M-protein are not measurable, a decrease of 25%–49% in the difference between involved and uninvolved FLC levels is required in place of the M-protein criteria.
 
• If present at Baseline, a 25%–49% reduction in the size of soft tissue plasmacytomas is also required
 

Stable disease	
 
• Not meeting criteria for CR, VGPR, PR, or PD
 

Approved

Footnotes defined on next page

Response Subcategory a	Multiple Myeloma Response Criteria
PD b	
Any one or more of the following:
 

• Increase of <math>\geq 25\%</math> from lowest response value in:

➢ Serum M-component and/or (the absolute increase must be <math>\geq 0.5</math> g/dL)

○ Urine M-component and/or (the absolute increase must be <math>\geq 200</math> mg/24 h)

○ Only in patients without measurable serum and urine M-protein levels; the difference between involved and uninvolved FLC levels. The absolute increase must be <math>>10</math> mg/dL

➢ Bone marrow plasma cell percentages (absolute percentage must be <math>\geq 10\%</math>)

• Definite development of new bone lesions or soft tissue plasmacytomas or definite increase in the size of existing bone lesions or soft tissue plasmacytomase, f, g

• Development of hypercalcemia (corrected serum calcium <math>> 11.5</math> mg/dL or <math>2.65</math> mmol/L) that can be attributed solely to the plasma cell proliferative disorder

Page 2 of 2

Source: Durie 2006; Rajkumar 2011 (modified for protocol purposes).

CR = complete response; sCR = stringent complete response; FLC = serum light chain; MR = minor response; PD = progressive disease; PR = partial response; SFLC = serum free light chain; VGPR = very good partial response

**Note:** Patients with measurable disease in both serum (SPEP) and urine (UPEP) at study entry are required to meet response criteria in both UPEP and SPEP in order to qualify for a MR or better. Conversely, it should be noted criteria for PD only needs to be met, and confirmed, in 1 parameter. For patients without measurable protein on UPEP at Baseline, UPEP will need to be repeated to confirm a response.

- a Patients with measurable disease in both serum (SPEP) and urine (UPEP) at study entry are required to meet response criteria in both UPEP and SPEP in order to qualify for a MR or better. Conversely, it should be noted that criteria for PD only needs to be met, and confirmed, in one parameter.
- b **All response categories (CR, sCR, VGPR, PR) require 2 consecutive assessments** made at any time before the institution of any new therapy, as well as no known evidence of progressive or new bone lesions if radiographic studies were performed. Radiographic studies are not required to satisfy these response requirements. Bone marrow, plasmacytoma, and skeletal survey assessments are not required to be confirmed by repeat testing. SD requires a duration of  $\geq 6$  weeks.
- c Presence/absence of clonal cells is based upon the  $\kappa/\lambda$  ratio. An abnormal  $\kappa/\lambda$  ratio by immunohistochemistry and/or immunofluorescence requires a minimum of 100 plasma cells for analysis. An abnormal ratio reflecting presence of an abnormal clone is  $\kappa/\lambda$  of  $> 4:1$  or  $< 1:2$ .
- d **Determination of PD while on study requires 2 consecutive assessments** made at any time before classification of PD and/or the institution of new therapy. Serum M-component increases of  $\geq 1$  g/dL from nadir are sufficient to define progression if nadir M-component is  $\geq 5$  g/dL.
- e Plasmacytomas: A definite increase in the size is defined as a  $\geq 50\%$  increase as measured serially by the sum of the products of the cross-diameters of the measurable lesion. A plasmacytoma is considered measurable if the longest diameter is at least 1 cm and the product of the cross diameters is at least 1 cm^2. Plasmacytomas of lesser size will be considered non-measurable.
- f The requirement for bi-directional measurements applies only to plasmacytomas.
- g The plasmacytoma specifications for PD are based on interpretation of the IMWG-URC and practical considerations for study execution.

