## 4. SUBJECT ELIGIBILITY

### 4.1 Inclusion Criteria

101. Subject has provided informed consent prior to initiation of any study-specific activities/procedures.
102. Age  $\geq$  18 years old

103. Pathologically-documented, definitively-diagnosed relapsed or refractory MM, NHL, or AML ([Appendix G](#)) and is intolerant to, or considered ineligible for available therapies known to provide clinical benefit.
- 104. MM subjects only:**
- Measurable disease per the IMWG response criteria ([Appendix E](#); assessed within 21 days prior to enrollment), as indicated by one or more of the following:
    - Serum M-protein  $\geq 0.5$  g/dL
    - Urine M-protein  $\geq 200$  mg/24 hours
    - For Subjects who do not meet 1 of the 2 prior criteria:
      - Serum Free Light Chain (sFLC)  $\geq 10$  mg/dL ( $\geq 100$  mg/L) **AND** an abnormal sFLC ratio ( $< 0.26$  or  $> 1.65$ ) as per the IMWG response criteria
- 105. NHL subjects only:**
- Radiographically measurable disease with a clearly demarcated nodal lesion at least 1.5 cm in its largest dimension or a target extranodal lesion at least 1.0 cm in its largest dimension
- 106. AML subjects only:**
- Pathologically confirmed diagnosis of AML as defined by the WHO Classification ([Appendix H](#))
  - More than 5% blasts in bone marrow
- 107. MM and NHL subjects only:**
- Hematological function, as follows without transfusion or growth factor support within 2 weeks prior to study day 1:
    - Absolute neutrophil count  $\geq 1.0 \times 10^9/L$
    - Hemoglobin  $> 8$  g/dL
    - Platelet count  $\geq 75 \times 10^9/L$

**NOTE for MM subjects only:** Platelet count  $\geq 50 \times 10^9/L$  (in subjects where  $< 50\%$  of bone marrow nucleated cells were plasma cells) OR  $\geq 30 \times 10^9/L$  (in subjects where  $\geq 50\%$  of bone marrow nucleated cells were plasma cells) without transfusion or growth factor support are allowed into the study.
108. Eastern Cooperative Oncology Group (ECOG) performance status of  $\leq 2$  ([Appendix F](#))
109. Life expectancy of  $> 3$  months, based on the opinion of the investigator
110. Able to swallow and retain orally administered medication and does not have any clinically significant gastrointestinal abnormalities that may alter absorption

Approved

111. Hepatic function, as follows:

- Aspartate aminotransferase (AST) and alanine aminotransferase (ALT) < 3 x upper limit of normal (ULN)

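### Appendix E gives myeloma CR no serum free-light-chain condition, so a subject measurable only by sFLC could be classed CR while failing the light-chain rules for MR and PR

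*Protocol*

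**What the plan says.** **Entry (Protocol 4.1, criterion 104).** A myeloma subject qualifies with serum M-protein of at least 0.5 g/dL or urine M-protein of at least 200 mg/24 hours. A third route, introduced by "For Subjects who do not meet 1 of the 2 prior criteria", accepts sFLC of at least 10 mg/dL with an abnormal ratio (below 0.26 or above 1.65).

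**Response (Protocol Appendix E).** CR has three conditions: "Negative immunofixation on the serum and urine"; "Disappearance of any soft tissue plasmacytomas"; and less than "5% plasma cells in bone marrow". At PR, when M-protein cannot be measured, a 50% "decrease in the difference between involved and uninvolved FLC levels is required in place of the M-protein criteria". VGPR has the parallel rule at 90%, "in the difference between the involved and uninvolved FLC levels required in place of the M-protein criteria". MR and PD have light-chain rules of their own. "Normal SFLC ratio" first appears at sCR, as an addition to CR.

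**Confirmation (Appendix E, footnote b).** Responses need two consecutive assessments and no known progressive or new bone lesions. However, "Bone marrow, plasmacytoma, and skeletal survey assessments are not required to be confirmed by repeat testing".

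**Use (SAP section 5).** ORR counts PR or better on investigator assessment. DOR runs from the first observation of response. For myeloma the SAP cites IMWG-URC and adds no light-chain rule.

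**The concern.** For an sFLC-only subject the light chain is the marker that made the disease measurable. Every lower response category, and progression, is tied to it. CR is not. Such a subject may already be immunofixation-negative and free of plasmacytomas before treatment. Two of the three CR conditions then hold at entry, and classification turns on one marrow result that need not be repeated. A subject could satisfy the top of the scale while missing its lower steps, so the categories are not ordered.

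At stake are the myeloma ORR, the tabulated best response and the start of DOR. The study is single-arm and open-label, groups are small and response is investigator-assessed, so one classification is visible in the reported rate.

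**Working it through.** **1. Subjects concerned.** Those below both M-protein thresholds who enter on sFLC. I assume these are the subjects Appendix E treats as having M-protein that is not measurable; the appendix does not define the term separately.

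**2. Appendix E rows side by side, for these subjects.**

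| Category | Serum light-chain condition |
|---|---|
| MR | involved-minus-uninvolved difference down 25–49% |
| PR | difference down at least 50% |
| VGPR | difference down at least 90% |
| CR | none |
| sCR | CR plus a normal sFLC ratio (and no clonal marrow cells) |
| PD | difference up at least 25% from the lowest value, absolute rise above 10 mg/dL |

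**3. Does anything else close the gap?**
- The Note and footnote a require response in both serum and urine electrophoresis where both were measurable. They do not mention light chains.
- Footnote b adds confirmation and the bone-lesion condition. It adds no light-chain condition.
- Footnote c concerns the kappa/lambda ratio of marrow cells, not serum.
- SAP section 5 adds nothing for myeloma.

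**4. Test case (illustrative values).** Entry: sFLC 30 mg/dL, abnormal ratio, serum and urine immunofixation negative, no plasmacytoma, marrow 8%. On treatment: sFLC 29 mg/dL, immunofixation negative on two consecutive assessments, no new or progressive bone lesions, one repeat marrow at 4%. Taking the uninvolved chain as negligible, the fall is (30 − 29)/30 = 3.3%.
- MR (25%): not met. PR (50%): not met. VGPR (90%): not met.
- CR: all three conditions met, with footnote b satisfied.
- Stable disease is defined partly by not meeting CR, so it does not take precedence.

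The marrow does change in this example. What it shows is CR without a light-chain response, not CR without any change in disease.

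**5. Size.** The exact (Clopper–Pearson) limits are the α/2 quantile of Beta(x, n − x + 1) and the 1 − α/2 quantile of Beta(x + 1, n − x).
- Protocol 10.3 states 5% to 45% for a 20% ORR in 10 subjects at 80% confidence. With x = 2 and n = 10 the result is 5.45% to 44.96%, which reproduces it.
- One added responder of this kind gives 3/10 = 30%, with 80% CI 11.6% to 55.2%. The shift is 1/10 = 10 points.
- SAP 3.2 states 6% to 44% for a 20% ORR in 20 subjects at 95% confidence. With x = 4 and n = 20 the result is 5.7% to 43.7%, which reproduces it. One more responder gives 5/20 = 25%, with 95% CI 8.7% to 49.1%. The shift is 1/20 = 5 points.

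The number of such subjects is unknown. None means no effect; each one adds 1/n.

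**The case against.** The strongest case against accepts the text and attacks its reach. Several parts of it stand.

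- **The subset is narrow.** Entering on sFLC means M-protein below a threshold, not negative immunofixation. CR also needs the marrow, plasmacytoma, bone-lesion and two-assessment conditions. A reader might infer that negative immunofixation alone is enough for CR; it is not.
- **The marrow is not scheduled.** Table 4, its footnote 18 and Protocol 7.2.10.6 call for a repeat myeloma marrow to confirm a CR. An investigator must first suspect CR, which is unlikely with sFLC nearly unchanged. A reader might infer that a subject with marrow below 5% at screening becomes a complete responder without any drug effect. The documents support only that such a subject could meet the written criteria if a marrow were repeated on treatment.
- **Versions differ.** The SAP implements protocol amendment 4; the Appendix E available is from Amendment 1. A reader might infer that Part 3C and its MRD-negative-at-CR proportion are affected. That follows only if the appendix is unchanged. Conversely, Group 2A with its 10 subjects belongs to the supplied protocol and is not among the parts listed in the SAP's redesign.
- **ORR is secondary and descriptive.** SAP 2.2 plans no hypothesis test, the intervals are already wide, and the 1/n shift would follow from any single misclassification.
- **The missing condition is not dictated.** Appendix E shows that CR lacks a light-chain rule, not which rule was intended.

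These points limit frequency, scope and wording. None supplies a light-chain condition for CR, and a written response definition should not depend on investigators declining to apply it.

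**Conclusion.** The gap is real in the supplied Appendix E. CR carries no sFLC condition, although sFLC-only subjects are eligible and the VGPR, PR, MR and PD rows all carry a light-chain rule for them. An sFLC-only subject could meet the written CR criteria while failing MR and PR, would count in ORR and would start DOR.

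The effect is 10 points of ORR per subject in a group of 10. The number of such subjects is not given and is probably small. In Part 3C the effect would be 5 points per subject in 20, plus entry to the MRD-negative-at-CR denominator, but only if amendment 4 kept this CR row, which cannot be checked here. The conclusion assumes that the rows are applied as written and that a repeat marrow is taken. It should be corrected: it is a stated rule that can misclassify response, and the repair is cheap.

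**What to change.** In the CR row of Appendix E, and in the SAP derivation of myeloma response, add a light-chain condition for subjects measurable only by sFLC. Options are a normal sFLC ratio on two consecutive assessments or, at minimum, the fall in light-chain difference already required for VGPR. If the ratio is chosen, sCR would still be distinguished by the absence of clonal marrow cells. Because a ratio can also normalise through a rise in the uninvolved chain, state explicitly that an sFLC-only subject who fails the PR light-chain rule cannot be classed CR.

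Limit the rule to these subjects. A reader might infer that no myeloma subject should rise above PR without a light-chain fall. Appendix E does not support that: its light-chain rules replace the M-protein rules only where M-protein cannot be measured, and a general rule could deny VGPR or CR to subjects followed by serum or urine M-protein.

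Check the amendment 4 appendix first; if it already has such a condition, only the SAP derivation needs to state it.

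Cost: one line in the appendix and one in the derivation. No new sample is needed, because sFLC and its ratio are already scheduled (Protocol 7.2.10.2). The myeloma CR rate or ORR may be slightly lower.
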